3.4 Safety Endpoint(s)

Safety evaluations include AE monitoring, physical examinations, vital sign measurements, and clinical laboratory testing (hematology, chemistry, and urinalysis) as measures of safety and tolerability. An internal DMC is monitoring safety at regular intervals.

4.0 Analysis Populations

The following population sets will be used for the analyses.

The Full Analysis Set (FAS) includes all enrolled subjects who received at least 1 dose of ravagalimab (including subjects randomized to ravagalimab prior to protocol Version 4.0). The FAS will be used for all efficacy and baseline analyses.

Subjects enrolled prior to protocol version 4.0 will be unblinded after they finish Week 8 assessments. Subjects who were randomized to and received ravagalimab will be included in the FAS.

The Safety Analysis Set consists of all subjects who received at least 1 dose of study drug. Subjects randomized to the study prior to Version 4.0 will be analyzed along with subjects enrolled after protocol Version 4.0 for safety analysis.

5.0 Subject Disposition

The total number of subjects who were enrolled (randomized), and treated will be summarized.

A summary of subject accountability will be provided where the number of subjects in each of the following categories will be summarized:

- Subjects enrolled (randomized) in the study;
- Subjects included in key analysis populations (FAS, Safety Analysis Set);
- Subjects who took at least one dose of study drug;
- Subjects who completed protocol-specified treatment;
- Subjects who prematurely discontinued study drug (all reasons and primary reason);

For end of study participation, the number and percentage of subjects who completed the protocol defined follow-up period (or did not with associated reasons) will be summarized.

6.0 Study Drug Duration and Compliance

For the FAS, duration of treatment will be summarized. Duration of treatment is defined for each subject as last dose date minus first dose date + 14 days. Duration of treatment will be summarized using the number of subjects treated, mean, standard deviation, median, minimum and maximum. In addition, the number and percentage of subjects in each treatment duration interval (1 to 14, 15 to 28, 29 to 42, 43 to 56, 57 to 84, and > 84 days) will be summarized.

Treatment compliance will be summarized for the entire treatment period for the FAS. Treatment compliance is defined as the number of injection actually taken divided by the number of injection that should have been taken. Percent compliance will be summarized.

7.0 Demographics, Baseline Characteristics, Medical History, and Prior/Concomitant Medications

Demographics, baseline or disease characteristics, medical history, and prior and concomitant medications will be summarized for the FAS. Categorical variables will be summarized with the number and percentage of subjects; percentages will be calculated based on the number of non-missing observations. Continuous variables will be summarized with descriptive statistics (number of non-missing observations, mean and standard deviation, median, minimum and maximum).

7.1 Demographics and Baseline Characteristics

Continuous demographic variables include

- Age (years),
- weight (kg),
- body weight – female (kg)

- body weight – male (kg)
- height (cm),
- height – female (cm)
- height – male (cm)
- body mass index (bmi) (kg/ m²).

Categorical demographic variables include

- sex (male, female),
- age (< 40, 40 - < 65, ≥ 65 years),
- ethnicity (Hispanic or Latino, not Hispanic or Latino)
- race (white, non-white),
- region (Europe, North America, or rest of world),
- tobacco user (current, former, never, unknown),
- alcohol user (current, former, never, unknown).

Continuous disease characteristics at baseline include

- full mayo score and its components (stool frequency, rectal bleeding, PGA and endoscopy subscores),
- partial mayo score,
- adapted mayo score,
- hs-CRP (mg/L),
- fecal calprotectin (mg/kg),
- albumin (g/L),
- UC disease duration in years,
- modified Baron score,
- UCEIS,
- Geboes score,
- number of extraintestinal manifestations.

Categorical disease characteristics include

- baseline steroid use (yes, no),
- baseline immunosuppressant use (yes, no),
- baseline aminosalicylates use (yes, no),
- prior exposure to biologic/JAK therapy for UC (1, >1)
- prior inadequate response/intolerance to biologic/JAK therapy for UC (1, > 1)
- prior exposure to biologic therapy for UC (1, >1),
- prior exposure to anti-TNF use for UC (yes, no),
- baseline hs-CRP (<=5mg/L, > 5mg/L),
- mayo endoscopic subscore (2, 3),
- adapted mayo score (<= 7, > 7),
- full mayo score (<= 9, > 9),
- disease duration (\leq 3 years, > 3 years),
- disease extent (left-sided, extensive/pancolitis, limited to rectum)

7.2 Medical History

Medical history data will be coded using the Medical Dictionary for Regulatory Activities (MedDRA). The actual version of the MedDRA coding dictionary will be noted in the statistical tables and clinical study report. The number and percentage of subjects in each medical history category (by MedDRA system organ class and preferred term) will be summarized. The system organ class (SOC) will be presented in alphabetical order, and the preferred terms will be presented in alphabetical order within each SOC. Subjects reporting more than one condition/diagnosis will be counted only once in each row (SOC or preferred term).

7.3 Prior and Concomitant Medications

Prior and concomitant medications will be summarized by generic name. A prior medication is defined as any medication taken prior to the date of the first dose of study drug. A concomitant medication is defined as any medication that started prior to the date

of the first dose of study drug and continued to be taken after the first dose of study drug or any medication that started on or after the date of the first dose of study drug, but not after the date of the last dose of study drug plus 84 days. The number and percentage of subjects taking medications will be summarized by generic drug name based on the World Health Organization (WHO) Drug Dictionary for both prior and concomitant medications.

8.0 Efficacy Analyses

8.1 General Considerations

UC-Related corticosteroids intercurrent events are defined as follows:

- subjects not on UC-related corticosteroids (systemic or locally acting corticosteroids for UC) at Baseline who initiated UC-related corticosteroids during the Induction Period;
- subjects on UC-related systemic corticosteroids at Baseline who had dosages increased to greater than the prednisone equivalent dose of corticosteroid at Baseline, or initiation of any rectal corticosteroids during the Induction Period regardless of rectal corticosteroid dose.

The time point of the UC-related corticosteroids intercurrent event is defined as the date when one of the scenarios above occurs for a subject. As such, subjects will be considered as "non-responder" for binary endpoints at or after the occurrence of the UC-related corticosteroids intercurrent event through the end of the Induction Period. For continuous endpoints, all measurements at or after the occurrence of the UC-related corticosteroids intercurrent event through the end of the Induction Period will not be used in the analysis.

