#### Why Is This Study Being Conducted

Ulcerative colitis (UC) is a chronic, relapsing inflammatory disease of the rectum and/or large intestine characterized by inflammation and ulceration of the mucosal and submucosal intestinal layers. The hallmark clinical symptoms include bloody diarrhea associated with rectal urgency and tenesmus. The clinical course is marked by exacerbation and remission. Extraintestinal complications include arthritis, erythema nodosum, pyoderma gangrenosum, uveitis, and primary sclerosing cholangitis. Conventional therapies for the induction of remission include 5-aminosalicylic acid (5-ASA) derivatives, corticosteroids and the immunomodulatory agent cyclosporine. 5-ASA derivatives as well as thiopurines are used for the maintenance of remission. The biological agents infliximab, adalimumab, golimumab, vedolizumab, and ustekinumab as well as the Janus kinase (JAK) inhibitor tofacitinib are indicated for the induction and maintenance of remission in subjects with moderate to severe UC. Despite increasingly available therapies, currently approved UC therapies have limited efficacy and have a potential for significant safety events. Thus, a large unmet need continues to exist for the treatment of UC.

CD40 is a tumor necrosis factor (TNF) receptor family member that plays an important role in lymphocyte activation and antigen presenting cell (APC) function. CD40 expression on epithelium, leukocytes, and vascular endothelium is elevated in systemic inflammatory diseases (e.g., Crohn's disease [CD], UC, rheumatoid arthritis [RA], and systemic lupus erythematosus [SLE]). Ravagalimab is a proprietary monoclonal antibody (mAb) that is a potent CD40 antagonist with no evidence of agonist activity.

Evidence from in vitro studies, preclinical models, and human disease suggests that CD40 signaling is important in the pathogenesis of UC and inhibition of CD40 mediated signaling may be a potential treatment for patients with UC. For further details, please see ravagalimab Investigator's Brochure.

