### 5.3 Prohibited Medications and Therapy

---

Except as listed in the eligibility criteria, the following medications are prohibited throughout the duration of the study:

- All biologics or small molecule medication (e.g., JAK inhibitors, sphingosine-1-phosphate [S1P] receptor modulators) with potential impact on UC
- Initiation of oral aminosalicylates, immunomodulators, IV or oral corticosteroids, and/or UC-related antibiotics through Week 12
- Cyclosporine, tacrolimus, or mycophenolate mofetil (unless for ocular application)
- Cannabis
- Rectal therapy with any therapeutic enemas or suppositories, with the exception of those required for endoscopy
- Apheresis
- Any parenteral nutrition
- Any investigational agent
- Any fecal microbial transplant

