## 5.4 Prior and Concomitant Therapy

---

Subjects taking oral aminosalicylates, immunomodulators, oral corticosteroids, and/or UC-related antibiotics at Baseline must continue their concomitant treatment for the duration of the induction period (through Week 12). Initiating and/or increasing doses of oral aminosalicylates, immunomodulators, oral corticosteroids, and/or UC-related antibiotics during the study is prohibited through Week 12. Decreasing doses of oral aminosalicylates, immunomodulators, oral corticosteroids, and/or UC-related antibiotics during the induction period is prohibited, except in the event of moderate-to-severe treatment related toxicities and after discussion with the AbbVie TA MD. Starting at Week 12 (maintenance period), oral aminosalicylates, immunomodulators, and/or UC-related antibiotics may be decreased or discontinued at the discretion of the Investigator. Starting at Week 12, initiating and/or increasing doses of oral aminosalicylates, immunomodulators, oral corticosteroids, and/or UC-related antibiotics is permissible after discussion with the AbbVie TA MD.

During the maintenance period, subjects can initiate an optional steroid taper at Week 12. While stopping the taper is permitted, increasing doses above the Baseline dose is permitted only after discussion with the AbbVie TA MD. Below is a suggested tapering schedule.

	Dose	Rate
Prednisone (or equivalent)	> 10 mg/day	5 mg/day per week
	≤ 10 mg/day	2.5 mg/day per week
Budesonide	≤ 9 mg/day	3 mg/day per week

Any questions regarding concomitant or prior therapy should be raised to the AbbVie emergency contact. Information regarding potential drug interactions with ravagalimab can be located in the ravagalimab Investigator's Brochure.

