## 5.5 Withdrawal of Subjects and Discontinuation of Study Drug or from Study Participation

---

A subject may voluntarily withdraw or be withdrawn from study participation, or be discontinued from study drug, at any time for reasons including, but not limited to, the following:

- Disease progression or lack of response to treatment.

- Clinically significant abnormal laboratory results or AEs, which rule out continuation of the study drug, as determined by the investigator or the AbbVie TA MD.
- The investigator believes it is in the best interest of the subject.
- The subject requests withdrawal from the study. This includes if a subject would like to discontinue after completion of the Week 52 visit.
- Eligibility criteria violation was noted after the subject started study drug and continuation of the study drug would place the subject at risk.
- Introduction of prohibited medications or dosages and continuation of the study drug would place the subject at risk.
- The subject becomes pregnant while on study drug.
- Subject has a malignancy, except for localized non-melanoma skin cancer. Discontinuation for carcinoma in situ of the cervix is at the discretion of the Investigator.
- Subject is significantly noncompliant with study procedures, which would put the subject at risk for continued participation in the trial.

Subjects who complete the induction period and do not achieve clinical response per Partial Adapted Mayo score at Week 12 will be discontinued.

For subjects to be considered lost to follow-up, reasonable attempts must be made to obtain information on the subject's final status. At a minimum, 2 telephone calls must be made and 1 certified letter must be sent and documented in the subject's source documentation.

AbbVie may terminate this study prematurely, either in its entirety or at any site. The investigator may also stop the study at his/her site if he/she has safety concerns. If AbbVie terminates the study for safety reasons, AbbVie will promptly notify the investigator.

During states of emergency or pandemic situations, it may be necessary to employ mitigation strategies to enable the investigator to ensure subject safety and continuity of care. Acceptable mitigation strategies are identified and included in the Operations Manual in [Appendix F](#).

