8.2 Handling of Missing Data

Missing data imputation will be done only for efficacy variables (categorical and continuous variables). For the analysis other than efficacy, no imputation will be done for missing values.

Censoring

For the time-to-event endpoint, i.e., time to clinical response per Partial Adapted Mayo score, missing data will be considered as censored at the last available time for the information.

Non-Responder Imputation incorporating Multiple Imputation to handle missing data due to COVID-19 (NRI-C)

The NRI-C will categorize any subject who does not have an evaluation during a pre-specified visit window (either due to missing assessment or due to early withdrawal from the study) as a non-responder for the visit. In addition, at or after the UC-related corticosteroids intercurrent event (see Section 8.1), subjects will be counted as non-responders. The only exception is that missing data due to COVID-19 infection or logistical restrictions related to the COVID-19 pandemic will be handled by Multiple Imputation (MI). At each visit, subjects will be characterized as responders or non-responders based on MI imputed values if missing due to COVID-19; otherwise, subjects will be considered as non-responders for missing due to other reasons in the NRI-C approach.

Mixed-Effect Model Repeated Measurements (MMRM)

MMRM analysis will be conducted using mixed-effect model including observed measurements at all visits. For the MMRM analysis, data collected at or after UC-Related corticosteroids intercurrent event will be excluded. The mixed model includes the categorical fixed effects of visit, baseline corticosteroid use (yes vs no), baseline Mayo endoscopic sub-score (2 vs 3), the continuous fixed covariate of baseline measurement and treatment and treatment-by-visit interaction, if applicable. An unstructured variance covariance matrix will be used. If there is a convergence issue, a compound symmetry structure and a variance components structure will be considered in sequence. The parameter estimations are based on the assumption of data being missing at random and using the method of restricted maximum likelihood (REML).

As Observed (AO)

The AO analysis will not impute values for missing evaluations, and thus a subject who does not have an evaluation on a scheduled visit will be excluded from the AO analysis for that visit. All observed data will be used in the analysis.

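### SAP 8.1/8.2 overrides an observed Week 8 response only after corticosteroid rescue, so a response reached after another prohibited UC therapy with plausible induction effect counts as a ravagalimab response.

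*SAP*

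**What the plan says.** **What overrides an observed value.** SAP 8.1 lists the events under "UC-Related corticosteroids intercurrent events are defined as follows": starting UC-related corticosteroids in subjects not on them at Baseline, raising the dose in subjects on systemic ones, or starting a rectal corticosteroid. SAP 8.2 makes a subject a non-responder under NRI-C for two reasons: no evaluation in the visit window (multiple imputation if the cause is COVID-19), or a visit "at or after the UC-related corticosteroids intercurrent event". SAP 8.3 adds only the friability re-scoring, which does not depend on therapy.

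**What is prohibited in induction.** Protocol 5.3 covers far more than steroids: "All biologics or small molecule medication" with potential impact on UC; "Initiation of oral aminosalicylates, immunomodulators, IV or oral corticosteroids, and/or UC-related antibiotics through Week 12"; cyclosporine, tacrolimus and mycophenolate; and therapeutic enemas or suppositories. Protocol 5.4 adds dose increases: "Initiating and/or increasing doses of oral aminosalicylates, immunomodulators, oral corticosteroids, and/or UC-related antibiotics during the study is prohibited through Week 12".

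**What the other analyses do.** The as-observed analysis states "All observed data will be used in the analysis". SAP Appendix A counts subjects who took a prohibited medication and does nothing further. SAP 4.0 uses the FAS for all efficacy analyses, and there is no per-protocol set.

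**The concern.** The SAP already accepts that a response after rescue should not be credited to ravagalimab, but applies this to one drug class. Protocol 2.1 says that the approved biologics and tofacitinib "are indicated for the induction and maintenance of remission in subjects with moderate to severe UC", and names 5-ASA derivatives and cyclosporine beside corticosteroids as conventional induction treatment. These therapies can therefore plausibly move a Week 8 endoscopic endpoint. The contrast is sharpest for rectal treatment: starting a rectal corticosteroid at any dose makes the subject a non-responder, while starting a rectal aminosalicylate, also prohibited, has no effect on coding. The SAP gives no reason for the difference.

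At stake is the primary estimate. It is one arm's response rate set against a low historical placebo rate, so no concurrent group would show the contribution of other therapy. The same coding carries into the binary secondary endpoints analysed with NRI-C.

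**Working it through.** **Step 1: can such a value reach the analysis?**

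- *On study drug.* Protocol 5.5 lists as a reason for withdrawal "Introduction of prohibited medications or dosages and continuation of the study drug would place the subject at risk". The trigger is tied to risk and is not automatic, so a subject can stay on drug and have the scheduled Week 8 endoscopy. Lack of response is also a listed reason, which removes some of these subjects.
- *Off study drug.* Protocol 5.6 keeps subjects in all scheduled visits. Protocol 6.2 contemplates standard-of-care therapy in such subjects, and Operations Manual 3.13 leaves treatment to the investigator. A subject who stops between Weeks 4 and 8 has the endoscopy at the premature discontinuation visit (Protocol Appendix D), preferably within 2 weeks, which leaves a new agent little time. The main remainder is a subject who stops before Week 4, starts another therapy and still attends Week 8.

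Both routes are open and both are narrow.

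**Step 2: the plan's own figure.** Protocol 7.3 gives about 3.1% as the chance that the posterior probability of a positive difference exceeds 90% when ravagalimab equals placebo, at N = 40. The placebo rate and prior are redacted, so this cannot be independently reproduced. An assumed 6% rate with prior weight 20 gives 3.09%, but so does 6% with weight 34 or 40. The match was found by scanning and does not identify the prior.

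**Step 3: size per subject.** 1/40 = 2.5 percentage points on the observed rate.

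**Step 4: illustration under assumed priors.**

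Inputs: visible placebo counts in SAP Appendix D1, (4 + 4 + 11)/(65 + 65 + 161) = 19/291 = 6.5%; weights up to 20, guided by the borrowing limit in SAP Appendix D2; ravagalimab prior Beta(0.5, 0.5).

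- Placebo: Beta(pw, (1 − p)w) for rate p and weight w. Ravagalimab after n responders: Beta(0.5 + n, 40.5 − n).
- k = smallest n with posterior P(difference > 0) > 0.90.
- Inactive drug, no rescue: P(X ≥ k | 40, p).
- One rescued subject with chance r of a subscore of 0 or 1: r·P(X ≥ k − 1 | 39, p) + (1 − r)·P(X ≥ k | 39, p).

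At 6.5% and weight 20, the posterior probability is 0.838, 0.891 and 0.928 for n = 5, 6 and 7, so k = 7. The base is P(X ≥ 7 | 40) = 1.40%. With P(X ≥ 6 | 39) = 3.95% and P(X ≥ 7 | 39) = 1.22%:

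- r = 0.3: 0.3 × 3.95 + 0.7 × 1.22 = 2.04%
- r = 0.5: 0.5 × 3.95 + 0.5 × 1.22 = 2.58%
- r = 1: 3.95%

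| Assumed rate, weight | k | No rescue | r = 0.3 | r = 0.5 | r = 1 |
|---|---|---|---|---|---|
| 6.5%, 20 | 7 | 1.40% | 2.04% | 2.58% | 3.95% |
| 6.5%, 10 | 8 | 0.38% | 0.60% | 0.77% | 1.22% |
| 6%, 20 (largest) | 6 | 3.09% | 4.40% | 5.49% | 8.22% |
| 8%, 10 (smallest) | 9 | 0.37% | 0.54% | 0.70% | 1.09% |

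Over rates of 4–8% and weights of 10, 15 and 20, one rescued subject adds 0.17 to 1.31 points at r = 0.3 and 0.72 to 5.13 points at r = 1. Every one-subject case stays below the 10% limit in SAP Appendix D2.

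**The case against.** The strongest reply is that the event is rare by design. These therapies are prohibited, and their use is a protocol deviation. A subject who needs a rescue biologic fits the lack-of-response reason for withdrawal, the early discontinuation endoscopy limits exposure, and a subject with no in-window evaluation is already a non-responder (COVID-19 reasons aside). This stands. It makes the effect small, but it does not supply the missing rule, and Appendix A itself plans for such deviations to occur.

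A second reply is comparability. The historical comparison depends on aligned endpoint definitions (Protocol 4.2), and the published counts cannot be recoded. A stricter rule on ravagalimab alone could bias the comparison downward. This stands too, and is why both rules need reporting.

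A reader might infer three stronger things that the documents do not support:

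- *That every therapy prohibited in 5.3/5.4 should trigger non-response.* Protocol 2.1 mentions thiopurines only for maintenance and says nothing of antibiotics. Section 5.3 also contains items such as cannabis and parenteral nutrition that are not UC-active treatment.
- *That the primary result is biased in favour of ravagalimab.* The documents do not say how the published trials coded rescue, so the net direction is unknown.
- *That one or two rescued subjects push the false positive rate past 10%.* At 6% and weight 20, raising every subject's response probability by 2.5 or 5 points gives 12.0% or 27.4%. That is a different scenario; one rescued subject gives at most 8.2%.

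**Conclusion.** The gap holds on the text. Followed exactly, SAP 8.1/8.2 counts as a ravagalimab response an observed in-window Week 8 subscore of 0 or 1 reached after a prohibited biologic, small molecule, cyclosporine or tacrolimus, or a new or increased aminosalicylate, and no planned analysis corrects it. Protocol 2.1 supports an induction effect for approved biologics, tofacitinib, 5-ASA and cyclosporine. Including tacrolimus rests on its being grouped with cyclosporine in 5.3.

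The consequence is modest: 2.5 points per subject, unknown and probably small frequency, uncertain net direction against the published counts. The operating-characteristic figures assume the redacted prior and treat 90% as a boundary. It is a planning threshold only, since Protocol Appendix E records that the success criterion was removed. In the matched M14-234 comparison NRI-C applies to both groups, so the point concerns mainly the primary Bayesian comparison. This is a cheap improvement to make before lock; the study's conclusions do not hinge on it.

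**What to change.** Outcome coding only; no change to what subjects may receive.

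1. In SAP 8.1, before database lock, extend the intercurrent event to the start, or increase above the Baseline dose, during induction of a named list: biologics and small molecules for UC, cyclosporine or tacrolimus, and aminosalicylates by any route. Score non-response from that date to the end of induction.
2. Apply the same rule to the subject-level M14-234 placebo data (SAP 8.3.5) where concomitant medication is available.
3. Report the Bayesian comparison under both the extended and the current steroid-only rule, because the published counts (4/65, 4/65, 11/161) cannot be recoded.
4. Immunomodulators and UC-related antibiotics may go in a sensitivity version. Leave out the items in Protocol 5.3 that are not UC-active.

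A minor separate clarification: the second steroid trigger names systemic steroids and a prednisone-equivalent dose, but the documents neither classify oral budesonide or beclomethasone nor give a conversion. The SAP should say how a dose increase or a systemic start is handled in a subject whose only Baseline steroid is one of these.

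Cost: a few lines of SAP text, an agreed drug list, and a flag from concomitant-medication data already collected. The reported rate may fall slightly, and the extended rule may be stricter than the one behind the published placebo counts. Reporting both shows how much the choice matters, though not which version is the more comparable.
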